## LIST OF ABBREVIATIONS

Abbreviation / Acronym	Full Wording			
AE	Adverse Event			
AR	Adverse Reaction			
CAT	COPD assessment test			
CD	Cluster designation (cell surface markers)			
CI	Chief Investigator			
COPD	Chronic Obstructive Pulmonary Disease			
CRF	Case Report Form			
СТА	Clinical Trial Authorisations			
DMEC	Data Monitoring and Ethics Committee			
EudraCT	European Clinical Trials Database			
EBV	Epstein-Barr Virus			
EQ-5D-5L	EuroQol quality of life questionnaire			
FEV1	Forced expiratory volume in 1 second			
FVC	Forced vital capacity			
GCP	Good Clinical Practice			
GMCSF	Granulocyte Macrophage Colony Stimulating			
	Factor			
GOLD	Global initiative in Obstructive Lung Disease			
HHV-4	Human Herpes Virus 4			
ICAM-1	Intra cellular adhesion marker 1			
IgA	Immunoglobulin A			
ICH	International Conference of Harmonisation			
IMP	Investigational Medicinal Product			
ISRCTN	International Standard Randomised Controlled Trial Number Register			
MHRA	Medicine and Healthcare Products Regulatory			
	Agency			
NICTU	Northern Ireland Clinical Trials Unit			
PI	Principal Investigator			
qPCR	Quantitative Polymerase Chain Reaction			
REC	Research Ethics Committee			
RSV	Respiratory Syncytial Virus			
SAE	Serious Adverse Event			
SAR	Serious Adverse Reaction			
SOPs	Standard Operating Procedures			
SUSAR	Suspected Unexpected Serious Adverse			
	Reaction			
TMG	Trial Management Group			

## **1 STUDY SUMMARY**

Chronic obstructive pulmonary disease (COPD) is a prominent disease associated with a downward spiral of progressive breathlessness and functional decline. This condition is projected to become the third most common cause of mortality worldwide within the next decade. The extensive pressure facing the health service behaves us to improve the outcome for this disease as the health system comes under increasing strain. There is no treatment that can meaningfully alter the course of deteriorating lung function or the time to death and future research urgently needs to focus on novel therapeutic measures for COPD sufferers. Only some smokers go on to develop COPD. Our research group and others have demonstrated high levels of Epstein-Barr virus (EBV) in the sputum and in the airway mucosa of patients with COPD using novel molecular diagnostic techniques. EBV is a gamma herpes virus. The virus usually has a latent phase, during which it resides in the B-lymphocytes. It has a shedding phase where it is released from the epithelium. This is generally uncommon in healthy subjects, however, it is frequently found in COPD. Other investigators have demonstrated EBV within bronchial epithelial cells using in-situ hybridisation techniques. Consequently it is hypothesised that persisting EBV infection in conjunction with cigarette smoke exposure could be implicated in the chronic airway inflammation seen COPD. EBV can be suppressed in a mouth ulcer condition called oral hairy leukoplakia (in immunocompromised patients). The medication used is valaciclovir which has been licenced for use since 1995. The aim of this study is to evaluate the safety of valaciclovir in subjects with COPD and whether EBV detected in the sputum of patients with COPD can be suppressed. We will also examine the effect of viral suppression on clinical symptoms, lung function and markers of airway inflammation in the blood and sputum.

The EBV suppression in COPD (EViSCO) study will be a randomised double-blind placebo-controlled clinical trial. The EViSCO trial will recruit subjects with COPD (GOLD classification 2 and 3) and EBV detectable in their sputum samples. Trial participants will receive either valaciclovir one gram three times daily or a matching placebo for a total of 8 weeks. Each participant will attend three separate clinic visits during the study (baseline assessment at 0 weeks followed by assessment at 4 and 8 weeks from enrolment). Participants will undergo measurement of lung function and provide blood and sputum samples during clinic visits. The study will recruit a total of 88 participants to the trial. We will also conduct an exploratory sub-study that will involve bronchoscopic evaluation of the airway epithelium before and after treatment. During flexible bronchoscopy washings, brushings and biopsies will be collected for analysis. Bronchial brushings will facilitate bronchial epithelial cell culture experiments. The exploratory bronchoscopy sub-study will recruit participants from the 88 patients already enrolled into the EViSCO trial on a voluntary basis.

Study Design:	Randomised Double Blind Placebo Controlled Trial
Study Aims and Objectives:	Safety of Valaciclovir in COPD
Study Intervention:	Valaciclovir
Concurrent Control:	Placebo
Primary Outcome:	
 
Safety: The incidence of serious adverse reactions (SARs)
 
Efficacy: EBV suppression measured by quantitative Polymerase Chain Reaction
 

Secondary Outcome:	
 
Change in Forced Expiratory Volume in 1 second (FEV1) from baseline to week 8
 
Participant compliance measured by total number of tablets administered as a proportion of total number of tablets supplied
 

Study Setting:	Belfast Health & Social Care Trust
Patient Population:	COPD patients (GOLD stage 2 &3)
Sample Size:	88 (44 in each group)
Examination Points:	Baseline, 4 and 8 weeks Bronchoscopy Sub-study Baseline and 8 weeks
Study Duration:	4 years

## **3 BACKGROUND AND RATIONALE**

## 3.1 Background Information

### Introduction

COPD is present in 10% of the population . It is a disease occurring predominantly in smokers. Yet only one in four smokers become affected. Some people who never smoke develop the disease . COPD is predicted to rise from the 6th commonest cause of death in the 1990's to the third commonest cause of death by 2020 . In 2002 it was calculated that 12.5% of medical admissions were COPD. In 2007 there were 9,500 hospital admissions in Northern Ireland, this rose to 12,000 admissions by 2011 (data from [name], Public Health Agency NI). Mortality remains high and high 90-day-mortality and readmission rates are seen following COPD admissions .

A recent analysis of stakeholders in the COPD outcomes based Network for Clinical Effectiveness and Research Translation (CONCERT) highlighted that the impact on patient centred health outcomes was the most important criterion for prioritising future research projects. There were four aspects of care examined, chronic care, care coordination, acute exacerbations and transitions in care (mild to severe). In chronic care of COPD, effectiveness of care and pharmaceutical treatment were selected as priorities .

*Inflammation*: COPD is characterised by inflammation with high levels of IL-8 and increased neutrophils in sputum. In previous studies it has been shown that IL-8 causes the neutrophils to cross the airway epithelium. The mechanism is by CD11b/CD18 on the neutrophils binding to epithelial ICAM-1. ICAM-1 is increased in COPD . The airway mucosa is infiltrated with CD8+ T lymphocytes (cytotoxic – suppressor cells).

**Chronic viral infection in COPD**: The finding of CD8+ T cells has lead researchers to investigate if there is evidence of a chronic viral infection in these individuals. Some have proposed that a component of adenovirus (early antigen -E1A) may be left from early infections in childhood , but evidence has been unable to be demonstrated for either E1A or persistent adenovirus infection . Two teams have proposed chronic and acute RSV infection in COPD . However this research group and a separate team in the United States, have been unable to demonstrate significant amounts of RSV using different primers.

**Epstein Barr virus (EBV) and COPD**: In the search for chronic viruses in COPD Epstein Barr virus (EBV) has been found in the sputum of several groups of patients, with differing degrees of disease severity . In the initial study, EBV was found in the sputum of half of the patients with severe COPD, a group of these patients were followed up at clinic after discharge and 20% lost their EBV and 20% who were negative for the virus began shedding EBV in their sputum . In the second study patients with early COPD disease who had never been exposed to inhaled or oral steroids were examined. We used a more sensitive assay and found EBV in the sputum of 75% of those with COPD . A third study by a separate research group

studied airway segments using antibodies against tissue samples (immunohistochemistry).

They found Epstein-Barr virus in the airway epithelium of patients with COPD . When examined by severity of disease 68% of patients with GOLD stage I and II COPD (mild disease), whereas 84% of GOLD stage III and IV patients (moderate and severe disease) had EBV in their airway epithelium. A low secretory IgA was identified and this was attributed to the cause of EBV in the airway. However, IgA is an anti-bacterial antibody- it is required for inoculation of EBV *into* lymphocytes . Epstein-Barr virus is lymphotropic virus which affects the B-cells. The relationship of EBV and low IgA is therefore likely to be causal (rather than low IgA causing proliferation of EBV). Indeed, in x-linked aggamaglobulinaemia patients are not infected with Epstein-Barr virus .

Epstein-Barr virus is present in most people, however it is confined to the B-cells. Occasionally it escapes the B-cells and enters the epithelial cells. Here it is in its shedding phase. All the studies to date have focused on high levels of the virus being shed in the airway- the epithelial shedding phase (see below), or being in the epithelium itself. A study of seroprevalence in military recruits found Epstein-Barr virus is more common in poorer socioeconomic groups and in smokers . Poorer smokers are the very group who go on to develop COPD . Furthermore, cigarette smoke promotes viral replication .

## Mechanism of Epstein Barr virus (EBV) infection in the airway epithelium;

Epstein Barr virus is a gamma herpes virus. It has a complex relationship with the human immune system. The virus has a latent and a shedding phase. When latent, it resides in the B-lymphocytes for years at very low copies (20-100 copies per million B-cells) . During the lytic phase, it infects the epithelial cells, which shed millions of viruses. Epstein-Barr virus latent membrane protein-1 induces CD54 (ICAM-1) on epithelial cells . ICAM-1 is the principal ligand for transmigration of neutrophils into the airway by binding neutrophil CD18/CD11b . ICAM-1 is also the receptor for human rhinovirus , which has been identified as the commonest cause of an acute exacerbation of COPD . Indeed, infection with rhinovirus then further increases ICAM-1. The bacterium H. Influenzae binds to ICAM-1 and is the most common pathogen in COPD 

Moreover, Epstein-Barr virus (EBV) infection is associated with increased GM-CSF synthesis by monocytes . These monocytes are inhibited from maturing by EBV , adding insult to injury, as the mature pulmonary macrophages are responsible for antigen presentation, a key immune regulatory role for infection. The GM-CSF activates neutrophils which more readily migrate across the endothelium  and the airway epithelium ([name] unpublished observations). However, Epstein-Barr virus causes increased apoptosis of these neutrophils . Thus, it is apparent that EBV, in its epithelial shedding phase, sets the scene for increased activation of the epithelium, propensity for further viral infection, adherence of H. Influenzae, failure of antigen presentation of bacteria and viruses as well as neutrophil recruitment to the airway followed by apoptosis. Furthermore, it has a deceptive technique to avoid appropriate antiviral responses by expressing LMP-1 (immediate early protein) and BZLF-1 which are located on the cell wall. These inhibit Interferon regulatory factor 7 (IRF-7) , subverting the synthesis of virus inhibiting interferon alpha and interferon beta.

## Evidence for Epstein-Barr virus suppression

#### Epstein-Barr virus suppression in Infectious mononucleosis

Tynell et al suppressed Epstein-Barr virus shedding in infectious mononucleosis by giving Aciclovir 800mg five times daily for 10 days in a placebo controlled trial . Active treatment was accompanied by Prednisolone (to help the inflammatory reaction during infection). Several earlier studies had similarly shown suppression of EBV shedding. A meta-analysis of 5 RCTs of acyclovir in Infectious mononucleosis showed that acyclovir caused a significant reduction in viral shedding on active treatment. However, when treatment was withdrawn there was a recurrence of viral shedding. There was a trend towards clinical effectiveness .

#### Epstein-Barr virus suppression in oral hairy leukoplakia

EBV is associated with oral hairy leukoplakia. This infection in the oral mucosa occurs often in immunosuppressed patients, especially with HIV. The appearance of oral hairy leukoplakia is an AIDS defining illness. It is associated with a decrease in Langherhan's cells . In an open labelled study Walling found that Valaciclovir 1g three times daily for 28 days suppressed viral shedding in 16 out of 19 cases (84%). There was a clinical and histological response of 89%. One patient failed treatment with Valaciclovir having recently failed high dose oral acyclovir treatment .

#### Epstein-Barr virus suppression in adults with normal immunity

A randomised trial in elite athletes compared Valaciclovir to placebo. There was an 82% reduction in virus shedding . A further study examined Epstein-Barr virus (HHV-4) in the B-cells of patients being treated for Herpes Simplex virus 2 (HSV-2). Patients were routinely given an induction course of Valaciclovir followed by a maintenance daily dose of Valaciclovir to suppress their herpes infection. In this study EBV was suppressed in the B-cell population .

### 3.2 Rationale for the Study

### Rationale for Epstein-Barr virus in COPD

EBV has been demonstrated in the airway of early and late COPD by the authors. In a separate study, the virus has been found in the airway epithelium of patients with mild, moderate and severe COPD. This is evidence of the virus being present across the spectrum of COPD. It is entirely reasonable to hypothesize that Epstein-Barr virus can be suppressed in the airway of patients with COPD.

#### Need for a trial now

COPD is a prominent disease with increasing prevalence . It is associated with a downward spiral of breathlessness. There is a need to avert the progression of this disease. Moreover, the extensive pressure facing the health service in winter behoves us to improve the outcome for this disease not only on behalf of the patients with COPD, but also for patients with other illnesses which are present during 'winter pressures' as the health system comes under strain. There is no treatment that can meaningfully alter the course of deteriorating lung function or the time to death.

## Rationale for the study population

Previous studies have shown that the majority of patients with mild, moderate and severe COPD have EBV in their airway, either in the epithelium or in the sputum. EBV has the ability to cycle from a shedding to a latent phase (where it stays in tiny amounts in the B-cells) . This study will evaluate the suppression of EBV shedding and we will therefore only study patients who are actively shedding with detectable virus in the sputum. We will study patients with COPD and moderate or severe airflow limitation on spirometry according to the current GOLD criteria (i.e. FEV1 <80% and >30% predicted). There is considerable overlap between patients with mild COPD and those with normal lung function. We will therefore not study patients with mild COPD. At the other end of the spectrum, very severe disease is associated with significant established organ damage, including hypoxia and often the cardiac complications of respiratory disease such as cor pulmonale. This cohort of patients may encounter significant difficulty enduring the rigors of the clinical trial. Consequently we will confine study participation to those with moderate and severe COPD.

## Rationale for the Drug

A meta-analysis has shown that aciclovir can suppress EBV shedding in Infectious Mononucleosis . Valaciclovir is the valine ester of aciclovir and is converted into acyclovir after absorption. Because of it's altered structure, absorption of valaciclovir is much higher than equivalent doses of aciclovir. The serum levels of acyclovir are 3-5 times higher after equivalent doses of valaciclovir compared to acyclovir. Oral valaciclovir achieves serum levels of acyclovir similar to high dose intravenous aciclovir .

### **Rationale for the Dose**

This is the first trial of valaciclovir in COPD. Previous studies which have used this drug to suppress Epstein-Barr virus in oral hairy leukoplakia and infectious mononucleosis have used a dose of 1 gram three times daily . Because of this precedent, this study will use the same dose.

### Rationale for the duration

The virus is usually suppressed after 2 weeks of treatment. In this study we will also examine the effect on inflammation in the airway. The duration of inflammation with a scar or with an asthma exacerbation is 6 weeks. This study will use 8 weeks treatment to firstly, suppress the virus, and secondly, to alter the inflammation.

## 4 STUDY AIMS AND OBJECTIVES

## 4.1 Study Hypothesis

The primary hypothesis is that treatment with valaciclovir is safe and will suppress Epstein-Barr virus in the sputum of patients with COPD.

## 4.2 Study Aim

This study seeks to establish if an antiviral therapy (valaciclovir) used to treat other herpes viruses is safe in patients with COPD. We will also examine whether it is possible to supress EBV in the airways of patients with COPD and examine important outcome measures including lung function and markers of airway inflammation in the blood and sputum.

In a sub-study airway samples will be obtained from patients with COPD by bronchoscopy before and after treatment with either valaciclovir or placebo.

## 4.3 Study Objectives

## The primary objective:

- To evaluate the safety of valaciclovir (1 gram three times daily for 8 weeks) for the suppression of Epstein-Barr virus in patients with COPD.
- To suppress Epstein-Barr virus shedding in COPD.

## The secondary objective:

- To determine the effect of Epstein-Barr virus (EBV) suppression on lung function (FEV1) in patients with COPD.
- To assess the tolerability of valaciclovir (1 gram three times daily for 8 weeks) by measuring participant compliance.

### The exploratory objectives:

[figure not shown]
- To measure the effect of EBV suppression on sputum and blood markers of inflammation in patients with COPD.
- To evaluate quality of life following EBV suppression in patients with COPD.

## 5 STUDY DESIGN

## 5.1 Study Design

The EViSCO trial is a randomised double-blind, placebo-controlled trial of 1 gram three times daily of valaciclovir or placebo for 8 weeks in COPD patients with Epstein-Barr virus. Patients will be randomised with an allocation ratio of 1:1 valaciclovir to placebo.

## 5.2 EViSCO Study Schematic Diagram

#### 5.3 Outcome Measures

### 5.3.1 Primary Outcome Measure

- The primary safety outcome is the incidence of serious adverse reactions (SARs).
- The primary efficacy outcome is suppression of Epstein-Barr virus in the sputum of subjects with COPD assessed using quantitative PCR at baseline and 8 weeks.

EBV is a DNA virus that may be suppressed beyond detection, however, it may be reverse transcribed and so it is possible that there will some detectable virus. For this this reason we will define EBV suppression as a 90% reduction in the viral load.

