## **10.1.1 Screening Visit Procedures**

The consent process will be conducted at the screening visit. Screening blood U&E samples will be taken (if required). Medical and Medication history will be reviewed, demographic data and screening sputum samples will be obtained. Patients in whom the screening sputum sample is found to be positive for EBV (measured by quantitative PCR) will be advised and invited to return for measurement of lung function. Those patients found to be eligible will then be invited to take part in the study. Patients who suffer an exacerbation of COPD in the interim period between the screening and baseline visits will be invited to be re-screened following clinical resolution of the exacerbation. Patients in whom sputum EBV qPCR is negative may be given the opportunity to return to be re-screened at a later date.

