### 10.1.2 Visit 1 (Baseline) Procedures

Medical history, medication history, vital signs and BMI will be recorded at the baseline visit. Participants will complete CAT and EQ-5D-5L assessments.. FBC, research blood and sputum samples will be taken. Participants will be asked regarding exacerbation status and if applicable exacerbations will be documented. Four weeks supply of the study drug or placebo will be given and an appointment for follow up will be made. The GP will be informed via written correspondence. Substudy volunteers will undergo diagnostic bronchoscopy.

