## **13 STATISTICAL CONSIDERATIONS**

### 13.1 Sample Size

A sample size of 31 subjects per group will have 90% power at a two-tailed significance level of 0.05 to detect a difference in the primary efficacy outcome EBV shedding of 70% in the treated group to 30% in the control group. With a dropout rate of approximately 30%, this study will require a total of 44 patients per group.

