## **Efficacy**

The number of patients experiencing suppression of Epstein-Barr virus in the two groups will be compared using Chi-Square test (or Fisher's exact if appropriate) followed by logistic regression adjusting for baseline FEV1 and other covariates if required. The odds ratio and 95% confidence interval will be reported.

The intention-to-treat basis analysis will use a significance level of  $\leq 0.05$  for the primary outcome. Per-protocol analysis will also be conducted which will involve a comparison of treatment groups that includes patients with overall study drug adherence of at least 70%. Subgroup analyses will be performed on the primary outcome for compliance. In order to assess differences in treatment effects between the subgroups we will report odds ratio and 99% CI from the treatment\*subgroup interaction model. Sensitivity analysis will be performed for the primary efficacy outcome excluding patients with a confirmed diagnosis of COVID-19

Additionally, change in viral load (Quantitative PCR) from baseline to week 8 in the two groups will be compared using independent t-test (or non-parametric alternative). The mean difference and 95% confidence interval will be reported.

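### Sputum EBV is scheduled for qPCR twice before treatment, but the viral-load comparison is an unadjusted t-test on change from one baseline and no EBV titre is a named covariate, so some precision is lost

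*Protocol*

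**What the plan says.** Two sputum samples are scheduled before study drug. Protocol 10.1.1 describes the first: "Patients in whom the screening sputum sample is found to be positive for EBV (measured by quantitative PCR"), who are then asked back for lung function. Protocol 10.1.2, headed as the baseline visit, describes the second: "FBC, research blood and sputum samples will be taken". Protocol Table 2 and SAP Table 1 both mark a sputum sample at screening and at Visit 1, and Protocol 10.2.1 sends trial sputum for EBV qPCR.

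The efficacy analyses refer to one baseline. Protocol 5.3.1 has the outcome "assessed using quantitative PCR at baseline and 8 weeks" and defines suppression as a 90% fall. SAP 7.1 adds that "change in viral load (Quantitative PCR) from baseline to week 8 in the two groups will be compared using independent t-test", or a non-parametric alternative. For suppression it plans a chi-square (or Fisher) test, then logistic regression on baseline FEV1 and further covariates if required. SAP 8.2 and 8.4 report titres at baseline, week 4 and week 8. No screening titre appears in any analysis or table, and no titre from any visit is named as a covariate.

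**The concern.** A single sputum titre is likely to be a noisy measure of a patient's usual level. Protocol 3.1 reports of earlier patients that "20% lost their EBV and 20% who were negative for the virus began shedding EBV in their sputum". The rationale for the study population describes the virus as cycling between shedding and latency. A change score carries all the noise of its baseline into the outcome. Regression on the baseline removes the part that does not predict week 8, and a second pre-treatment value may remove more.

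At stake is the width of the interval for the viral-load effect and, to a small degree, the power of the adjusted suppression model, in a trial that plans on about 62 evaluable patients.

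**Working it through.** **The plan's own figure.** Protocol 13.1 states "A sample size of 31 subjects per group", which "will have 90% power at a two-tailed significance level of 0.05", for "EBV shedding of 70% in the treated group to 30% in the control group". I read these rates as proportions suppressed, since more shedding on active drug would run the wrong way. With pooled variance and no continuity correction:

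n = [1.96·√(2·0.5·0.5) + 1.2816·√(0.7·0.3 + 0.3·0.7)]² / 0.4² = (1.386 + 0.831)² / 0.16 = 30.7, so 31.

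Power at 31 is 90.3%. For dropout, 31/0.7 = 44.3, against 44 stated; 44 × 0.7 = 30.8 evaluable gives 90.1%. The plan reaches its stated power without any covariate.

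**Assumptions for the gain.** The documents give no SD, no correlation and no screening-to-Visit 1 interval. I take log10 titres with equal variance (set to 1) and correlation r between Visit 1 and week 8, varied from 0.3 to 0.7.

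**Step 1: change t-test to ANCOVA on the Visit 1 titre.**
- Variance of change: 2(1 − r).
- Residual variance given Visit 1: 1 − r².
- Ratio: (1 + r)/2.

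**Step 2: adding the screening titre, all three correlations equal.**
- Residual variance given both: 1 − 2r²/(1 + r).
- Ratio to the one-titre model: [1 − 2r²/(1 + r)]/(1 − r²).
- With 62 patients, the extra parameter takes residual degrees of freedom from 59 to 58, so I multiply by 59/58 = 1.017 as an approximate penalty.

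| r | Step 1 ratio | Step 2 ratio | Step 2 with penalty |
|---|---|---|---|
| 0.3 | 0.65 | 0.947 | 0.963 |
| 0.5 | 0.75 | 0.889 | 0.904 |
| 0.7 | 0.85 | 0.830 | 0.845 |

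Simulation at 31 per arm agrees: about 12–36% lower variance from step 1, and a further 4–15% from step 2 under equal correlations.

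**Step 3: correlation that fades with time.** The extra R² from screening (S), given Visit 1 (V), for week 8 (W) is (ρ_SW − ρ_SV·ρ_VW)²/(1 − ρ_SV²). Under first-order decay ρ_SW = ρ_SV·ρ_VW, so the numerator is zero. Only the lost degree of freedom remains, about 2% more variance. With partial decay the simulated gain was about 0–2.5%.

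**Step 4: the binary endpoint.** With 31 per arm and an assumed 30% v 60% suppressed (the 60% is not in the documents), simulated power was 72–75% for logistic regression with the Visit 1 titre and 74–77% with both. At the planned 30% v 70% it was 92–94% and 94%. In those runs type I error with both titres was 5.5–6.5%, so part of the difference comes from a slightly liberal test. Once type I error is matched, the second titre adds about 0–2 points.

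**The case against.** A single baseline at the visit labelled as such is conventional and valid. SAP 7.1 allows further covariates if required, and SAP 7 allows ANCOVA after the t-test on the same terms, so a titre is unspecified rather than excluded. That stands, but a covariate chosen after the data are seen does not replace a prespecified one.

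Three stronger readings are tempting, and the documents do not support them.

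- **That the screening titre is worth a firm 8–17% of variance** (step 2 for r from 0.4 to 0.7, before the penalty). This needs screening to predict week 8 as well as Visit 1 does, although it is the earlier sample. The lower bound is zero or slightly below.
- **That the trial already holds two numeric titres for every randomised patient.** Sputum is spontaneous, so a sample may be missing. Protocol 10.1.1 uses the screening result as a positive/negative gate, and neither document says its number reaches the database. Re-screening is allowed, so some patients may have several screening samples.
- **That the protocol measures how unstable titres are in this population.** The 20% figures are positive/negative results in patients with severe COPD followed up after discharge, before the more sensitive assay described next. They show fluctuation but give no correlation for patients free of exacerbation for a month.

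It is also fair to object that covariates leave the headline chi-square test untouched, and that keeping Visit 1 as the reference leaves chance-high and chance-low baselines in the responder definition. Both are true. The gain lies in the viral-load analysis and the adjusted odds ratio.

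**Conclusion.** The point holds as lost efficiency. A reader might infer bias or an underpowered trial. Neither follows: baseline noise falls on both randomised arms alike, and 31 per group gives 90.3% power at the planned rates.

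Most of the available gain comes from the Visit 1 titre: about 12–36% lower variance than the change t-test for r from 0.3 to 0.7. The screening titre is secondary, ranging from about 2% worse under first-order decay to about 15% better under equal correlations, with about 0–2 power points for suppression. All these sizes rest on assumed correlations, log10 titres and about 62 evaluable patients. The change is worth making because it is cheap and leaves the endpoint alone.

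**What to change.** In SAP 7.1 and 8.4:

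- Analyse log10 viral load at week 8 by ANCOVA, with treatment, log10 Visit 1 titre and log10 screening titre as fixed terms, in place of the unadjusted t-test on change.
- Enter the same two titres in the planned adjusted logistic model for suppression.
- Keep Visit 1 as the reference for the 90% fall, and say so explicitly. Keep the chi-square test as planned. The screening titre should not become the reference: it is selected to be positive, and in simulated scenarios it sat 0.04 to 0.36 log10 above Visit 1.

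Fix three rules before unblinding:

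- the qualifying screening sample is the most recent positive one;
- one substitution value applies to all non-detects (the SAP baseline table has a row for EBV absent, so they are foreseen);
- if the numeric screening titre is missing, the models use the Visit 1 titre alone.

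The cost is SAP wording, a check that the screening titre is in the database, and one more parameter than a Visit 1-only model at about 62 evaluable patients. No new sample, visit or patient is needed.
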